9.4.4 SAFETY ANALYSES

Safety data will be presented by treatment group to the Data and Safety Monitoring Board during the course of the trial. Each adverse event will be displayed showing AE name per the CTCAE v5.0 when applicable, class, severity grade, random patient ID, clinic, treatment group, time since randomization, resolution status and physician’s assessment of relatedness to treatment. Participant-specific summary tables including any adverse event (yes vs no), frequency of multiple adverse events (i.e., 0, 1, 2, 3+) and highest severity grade of adverse event (none, mild, moderate, severe, life-threatening) will be displayed by treatment group along with p-values from Fisher’s exact tests.

In addition, rates of adverse events and hospitalizations will be reported between treatment groups, both by number of events and by participant. Count data will be analyzed using a negative binomial model accounting for over-dispersion of the count data.

Other safety data to be monitored include baseline levels and changes in laboratory measures, weight, and ECG results. These will be compared between treatment groups using ANCOVA models for change in measures or Fisher’s Exact Tests for categorical outcomes.

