1. Gastroparesis Cardinal Symptom Index (GCSI) total score;
GCSI is comprised of the first 9-items of the PAGI-SYM questionnaire.
2. Four PAGI-SYM questionnaire subscores: nausea/vomiting (3 items: nausea, retching, vomiting), bloating (2 items: bloating, stomach visibly larger), upper abdominal pain (2 items: upper abdominal pain, upper abdominal discomfort), GERD (7 items: heartburn during the day, heartburn when lying down, feeling of discomfort inside chest during the day, feeling of discomfort inside chest during sleep, regurgitation or reflux during the day, regurgitation when lying down, bitter, acid or sour taste in mouth)
3. Eight single-item PAGI-SYM questionnaire symptom severity scores: nausea, vomiting, stomach fullness, inability to finish a normal-sized meal, feeling excessively full after meals, loss of appetite, bloating, upper abdominal pain
4. Gastrointestinal Symptom Rating Scale (GSRS) total score
5. Clinical Patient Grading Assessment Scale (CPGAS) score
6. Patient Assessment of Upper Gastrointestinal Disorders-Quality of Life (PAGI-QOL) questionnaire total score
7. Hospital Anxiety and Depression Scale (HADS) questionnaire anxiety score and depression score
8. Patient Health Questionnaire 15 Somatic Symptom Severity Scale (PHQ-15) questionnaire total somatization score
9. SF-36v2 Quality of Life questionnaire Physical Component Score and Mental Component Score
10. Percent gastric emptying retention at 2 and 4-hours.
11. Anthropometric measurements (Body Mass Index (BMI)/ weight, waist circumference) (safety)
12. ECG measures (safety)
13. Laboratory measures (ALT, creatinine, glucose) (safety)
14. Frequency of side effects and adverse events, as well as severity of adverse events. (safety and tolerability)

Exploratory/Ancillary Outcomes: These outcomes either use novel techniques (items 1, 2, and 3) or are outcomes that have lower statistical power yet might provide insight into paths for future research (items 4,5). The outcome measures are changes over 4 weeks (week 4 minus baseline) in:

1. Intragastric meal distribution (IMD) as a measure of Fundic Accommodation (FA) using digital analyses of the GES test images
2. Gastric dysrhythmia and volume of water consumed until full measured with electrogastrogram (EGG) with water load satiety test

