9.2 SAMPLE SIZE DETERMINATION

Summary of sample size and computation of primary outcome:

The primary outcome variable is change in the PAGI-SYM postprandial fullness/early satiety subscore from baseline to 4 weeks. This subscore is calculated by averaging the scores for 4 PAGI-SYM items: stomach fullness, inability to finish a normal-sized meal, feeling excessively full after meals, and loss of appetite. Each item score ranges from 0 (none) to 5 (very severe) on an ordinal scale. The 4-item average is treated as continuous in the primary ANCOVA analysis of change and for sample size purposes.

The planned 108 participants sample size for this trial was derived using the following assumptions and methods:

- 2 equal size groups
- Power=90%
- Type 1 error (2-sided) = 0.05
- Two-sided tests
- Sample size increased by 10% to allow for 10% loss in primary outcome measure
- Placebo group assumptions: Based on the APRON RCT placebo data [9], we assumed that:
 - Mean (SD) change in postprandial fullness/early satiety subscore at 4-weeks = 3.7 (0.8)
 - Change from baseline at 4-weeks of fullness/early satiety subscore = -0.7 (1.0)
 - Correlation of postprandial fullness/early satiety subscore at baseline and 4-weeks = 0.55
- Method of analysis = ANCOVA of the change in the primary outcome score controlling for baseline value of the primary outcome score
- Intention-to-Treat Analysis using all randomized participants, corrected for missing outcome data:
 - Multiple imputation of the ANCOVA model using the chained equations method with 50 imputations using the Stata Software Command: *mi*
- Minimal Clinical Important Difference (MCID) = 0.62 SD (0.5 subscore points)
- Sample size software: Stata Software Command: *power repeated*
- **Sample size = 108 total (54 per group)**

Sample size for the primary outcome varying the MCID

MCID in SD units	0.3 SD	0.50 SD	0.62 SD*	1 SD
MCID subscore units	0.24	0.4	0.5	0.8
Total sample size	460	168	108	42
Number per group	230	84	54	21

* MCID between investigator-related severity and fullness/early satiety subscore range=0.62-0.70 SD [25]

For the key secondary outcome, symptom improvement by 1-point or more in the PAGI-SYM GSCI total score from baseline to week 4, we determined that the total sample size of 108 participants (54 per group) gives 80% power to detect an MCID for a relative improvement ratio=1.8 (60% buspirone vs. 32% placebo based on APRON

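### Highest adverse event severity grade is an ordered safety outcome, but the plan compares it only by an unordered Fisher's exact test; an ordinal estimate should be added beside it

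*Combined protocol and SAP*

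**What the plan says.** Item 14 of the secondary outcomes (Synopsis and section 3) is "Frequency of side effects and adverse events, as well as severity of adverse events", marked as a safety and tolerability outcome.

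Section 9.4.4 plans three participant-level tables by arm: any event (yes or no), "frequency of multiple adverse events (i.e., 0, 1, 2, 3" or more), and the "highest severity grade of adverse event (none, mild, moderate, severe, life-threatening) will be displayed by treatment group along with p-values from Fisher’s exact tests". A separate paragraph of 9.4.4 adds that "Count data will be analyzed using a negative binomial model accounting for over-dispersion of the count data".

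For severity, the Fisher p-value is the only between-arm comparison named. Section 9.4.3 promises an adjusted mean difference with a confidence interval for continuous secondary outcomes and an odds ratio with a confidence interval for binary improvement in the GCSI. It says nothing on severity. The sample size section gives "Sample size = 108 total (54 per group") and "Type 1 error (2-sided) = 0.05". It gives no event rates, effect size or power for any safety comparison.

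**The concern.** Highest severity grade runs from none to life-threatening, so its order carries information. Fisher's test on a 2 × 5 table gives the same p-value however the five columns are arranged. A steady drift towards worse grades under buspirone is therefore spread over four degrees of freedom instead of being gathered into one.

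Two things follow. For a general worsening, the test is less likely to show it than one that uses the order. And whatever the p-value, the reader gets no estimate of which arm fared worse or by how much, although the plan supplies such estimates for its efficacy outcomes. In a trial of 108 people, an interval for severity tells the reader more than a non-significant p-value does.

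**Working it through.** **Inputs from the documents.** 54 per arm (9.2); five grades and Fisher's exact test (9.4.4); two-sided 0.05 (9.2, stated for the sample size and assumed here for safety p-values, since no separate level is given).

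**The plan's own figure.** There is no safety power to reproduce. The 54 per arm can be recovered from 9.2. With SD 0.8 and correlation 0.55, the variance of change is 2 × 0.8² × (1 − 0.55) = 0.576. Then n per arm = 2 × (1.960 + 1.282)² × 0.576 / 0.5² ≈ 48.4, so 49, or 98 in total, and 98 × 1.10 ≈ 108. This bears only on the primary outcome.

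**Assumptions, not in the documents.** Placebo distribution over none, mild, moderate, severe and life-threatening: 60/20/13/6/1%, with 55/25/13/6/1% as an alternative. Harm is a common odds ratio (OR) for a worse grade: at each cut-point the cumulative odds of being at or below that grade are divided by OR.

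Example at OR 2:
- None: odds 0.60/0.40 = 1.5, halved to 0.75, so probability 0.75/1.75 = 0.429.
- Mild or less: odds 0.80/0.20 = 4, halved to 2, so probability 0.667, and mild = 0.667 − 0.429 = 0.238.
- Continuing, buspirone is 42.9/23.8/20.2/11.1/2.0%.

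**Tests compared.** Fisher's exact test extended to 2 × 5: the p-value is the summed probability of all tables with the same margins that are no more likely than the one observed. Against it, the tie-corrected Wilcoxon rank-sum test. Under no effect, with the 55% distribution, rejection was 5.2% and 5.0%, so both hold their level.

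**Power, 60% of placebo event-free, 54 per arm**

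| OR | Fisher | Rank-sum | Difference (points) |
|---|---|---|---|
| 1.5 | 12.5% | 19.2% | 7 |
| 2 | 31.3% | 47.0% | 16 |
| 2.5 | 52.1% | 70.6% | 19 |
| 3 | 69.6% | 85.8% | 16 |
| 3.5 | 82.2% | 93.4% | 11 |
| 5 | 96.8% | 99.3% | 3 |

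With 55% event-free, repeated simulations gave 31% to 33% against 47% to 50% at OR 2, about 53% against 72% at OR 2.5, and 71% against 87% at OR 3. The gap at OR 1.5 is about 8 points.

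**Sensitivity to the event rate, OR 2**

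| Placebo event-free | Fisher | Rank-sum | Difference (points) |
|---|---|---|---|
| 40% | 32.0% | 50.4% | 18 |
| 75% | 25.3% | 39.7% | 14 |
| 85% | 19.1% | 29.7% | 11 |
| 90% | 14.5% | 22.7% | 8 |

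**Harm that is not a uniform shift**
- 60/20/13/6/1% against 60/7/13/18/2% (mild becomes severe, any-event rate unchanged): Fisher 57%, rank-sum 10%.
- The same kind of move with 40% event-free: Fisher 35%, rank-sum 14%.
- A 20-point rise in mild events only (60% event-free): Fisher 53%, rank-sum 36%.
- A 15-point fall in event-free participants, almost all going to severe (60% event-free): Fisher 47%, rank-sum 50%.

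**Event counts.** With negative binomial counts, placebo mean 0.7, dispersion 1 and rate ratio 2: Fisher on the four categories 50%, rank-sum 61%, the planned negative binomial model 73%.

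Simulation error on a difference is about 1 point with 5,000 trials, 1 to 2 points with 1,500, and about 2 points for the count runs.

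**The case against.** **The size is assumed.** True: the documents give no rates, and section 8.2 expects most buspirone events to be infrequent to rare. A reader might infer that the plan simply gives up 15 to 20 points of power to see harm. The documents do not support that. The figure needs a roughly uniform shift with an odds ratio near 2 to 3. It is smaller for weaker or very strong effects and when events are rare.

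**Fisher may be the better test.** It can be, and for a pattern that matters: mild events becoming severe. The any-event comparison cannot see that shift either. A reader might infer that Fisher should be replaced, but the results above argue only for an addition.

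**The rest of the plan helps.** In part. A reader might extend the criticism to the event-count table, but the negative binomial model uses the full count and outperformed both other tests in every harm scenario run. The any-event test also picks up some of a general shift. At OR 2 with 75% event-free it has 31% power, against 25% for Fisher on grade and 40% for rank-sum. It says nothing about severity itself.

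**These are descriptive tables.** Also fair. The plan sets no safety decision rule and no intended conclusion of no difference. Each event is listed with grade, arm and relatedness, and events above grade 2 go to the Medical Safety Officer. A reader might infer that the plan is set up to declare the drug safe wrongly; nothing in it says so. What stands is that a listed secondary outcome has no planned estimate and no analysis that uses its order.

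**Conclusion.** The point holds as a cheap improvement, not as an error that endangers the trial. Highest severity grade is compared only by a test that ignores order and gives neither direction nor size. Under an assumed common odds ratio of 2 to 3, 54 per arm and 55% to 60% of placebo participants event-free, the ordinal test gains about 15 to 20 points of power. The gain is about 7 to 8 points at an odds ratio of 1.5, and about 11 points at 2 with 85% event-free. It reverses for some non-uniform harms. The missing estimate and interval do not depend on any of these assumptions. The event-count analysis is adequate as planned.

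One small labelling matter: the severity list in 9.4.4 ends at life-threatening, while 8.3.2 counts death among serious outcomes and 8.3.6 has reporting times for fatal events. A death would appear in the event listing but has no category of its own in the summary table.

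**What to change.** In 9.4.4, keep the Fisher p-values and add one sentence: for highest severity grade, the common odds ratio for a worse grade (buspirone against placebo), from a proportional-odds model with treatment as the only term, will be reported with its two-sided 95% confidence interval. An exact Wilcoxon or linear-by-linear test is an acceptable alternative if only a p-value is wanted, but it would not give the effect size.

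Leave the event-count analysis as it is. Optionally add a fatal category to the severity table.

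The cost is one sentence and one further nominal p-value in the safety table. A single odds ratio can hide a shift that is not uniform across grades. That is why the full table and the Fisher test should stay beside it.

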1 PROTOCOL SUMMARY

1.1 SYNOPSIS

Title: Buspirone for Early Satiety and Symptoms of Gastroparesis: A Multicenter, Randomized, Placebo-Controlled, Double-masked Trial (BESST).

Study Description:

This is a multi-center, randomized, double-masked, placebo-controlled, parallel treatment groups phase 2 trial to determine whether buspirone, a 5-HT 1a receptor agonist, can improve early satiety and postprandial fullness in participants with symptoms of gastroparesis and with at least moderately severe symptoms of early satiety and/or postprandial fullness. After enrollment, participants aged 18-85 years will be treated with buspirone (10 mg three times per day) or a matching placebo for 4 weeks, followed by a 2-week post-treatment washout period. The primary outcome for the study is the 4-week change (week 4 minus baseline) in the 4-item postprandial fullness/early satiety subscore (higher scores indicate worse symptoms) from the Patient Assessment of Gastrointestinal Disorders Symptom Severity Index (PAGI-SYM) questionnaire. We hypothesize that 10 mg t.i.d. buspirone treatment will reduce mean postprandial fullness/early satiety symptom severity subscores over 4-weeks compared to treatment with placebo.

Objectives:

Primary Objective: To determine whether 4 weeks of treatment with buspirone, a 5-HT 1a receptor agonist, compared to treatment with placebo improves symptoms of postprandial fullness and early satiety as indicated by the change in the PAGI-SYM questionnaire's postprandial fullness/early satiety subscore (score at 4-weeks minus score at baseline).

Secondary Objectives: To determine whether 4 weeks of treatment with buspirone compared to treatment with placebo improves overall and other gastroparesis symptoms, and other participant clinical characteristics (gastric retention, anxiety, depression, quality of life) and to determine the safety and tolerability of buspirone in adult participants with gastroparesis symptoms and at least moderate symptoms of postprandial fullness and early satiety.

Outcomes:

Primary Outcome: The primary outcome is the change in the postprandial fullness/early satiety subscore from baseline to 4 weeks; this subscore is calculated by averaging the scores for 4 PAGI-SYM questionnaire items: stomach fullness, inability to finish a normal-sized meal, feeling excessively full after meals, and loss of appetite.

Secondary Outcomes: Changes over 4-weeks (week 4 minus baseline) in:

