The secondary objectives have been selected to provide further information on whether 4-weeks of treatment with buspirone compared to treatment with placebo improves overall and other gastroparesis symptoms, and other participant clinical characteristics (gastric retention, anxiety, depression, quality of life) and to determine the safety and tolerability of buspirone in adult participants with gastroparesis symptoms and with at least moderate symptoms of postprandial fullness and early satiety.	Changes at 4 weeks from baseline in the following measures: (calculated as score at 4-weeks minus score at baseline in: 1. GCSI total score 2. Four other PAGI-SYM questionnaire subscores: nausea/vomiting (3 items: nausea, retching, vomiting), bloating (2 items: bloating, stomach visibly larger), upper abdominal pain (2 items: upper abdominal pain, upper abdominal discomfort), GERD (7 items: heartburn during the day, heartburn when lying down, feeling of discomfort inside chest during the day, feeling of discomfort inside chest during sleep, regurgitation or reflux during the day, regurgitation when lying down, bitter, acid or sour taste in mouth) 3. Eight single-item PAGI-SYM symptom severity scores: Nausea, vomiting, stomach fullness, inability to finish a normal-sized meal,	These outcomes were selected because they measure important gastroparesis symptoms or comorbidities of gastroparesis and are useful for determining if buspirone improves other symptoms commonly associated with gastroparesis and that buspirone is safe to use in adult gastroparesis patients.

OBJECTIVES	OUTCOMES	JUSTIFICATION FOR OUTCOMES

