9.4.3 ANALYSIS OF THE SECONDARY OUTCOME(S)

- Analysis of secondary outcomes are not dependent on findings of the primary endpoint
- Intention-to-Treat (ITT) Analysis Dataset (i.e., all randomized participants)
- Complete-Case Dataset

The analyses of secondary and exploratory outcomes are not dependent on findings of the primary outcome. The ITT Analysis Dataset will be used for any binary efficacy outcomes, and for continuous efficacy outcomes with 10% or more of the participants having missing data for the 4-week outcome. In that case, the ITT Analysis Dataset using multiple imputation with chained equations method modeling missing data on treatment group and baseline value of the outcome using 50 datasets will be done. Otherwise, the Complete-Case dataset may be used to analyze the continuous secondary efficacy outcomes and all safety outcomes. Except for improvement in GCSI total score defined as being 1 or more points less at 4-weeks than at baseline, and some safety measures (adverse event counts), the other secondary outcomes are continuous changes from baseline at 4-weeks.

Secondary outcomes are listed in [section 9.1](#). Assumptions will be checked and models checked post-estimation of the regressions as stated in [section 9.4.3](#).

The “main” secondary outcome is the change in the total GCSI score. This will be analyzed as both a continuous change variable, and also as the binary improvement variable using a logistic regression model regressing improvement on treatment group and the baseline value of the total GCSI. Relative Odds, two-sided 95% confidence intervals and a significance level computed using a likelihood ratio test will be reported.

The analysis of secondary outcomes will use complete-case analysis of covariance (ANCOVA) models for continuous outcomes, regressing the change from baseline in outcome at 4-weeks on an indicator variable for treatment group and the baseline value of the outcome. The treatment group difference in adjusted mean change will be presented, along with a two-sided 95% confidence interval, and P-value for each secondary outcome from the ANCOVA model for the between-groups difference in the means. P-values will be nominal, and not be adjusted for the multiplicity of secondary outcomes.

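### Section 9.4.4 compares participant-level adverse events and categorical safety outcomes by Fisher p-value alone; with 54 per arm a non-significant result cannot support a safety statement without a risk difference and interval

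*Combined protocol and SAP*

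**What the plan says.** The synopsis (section 1.1) makes it a secondary objective "to determine the safety and tolerability of buspirone in adult participants with gastroparesis symptoms". Secondary outcome 14 is "Frequency of side effects and adverse events, as well as severity of adverse events. (safety and tolerability"). In the section 3 table, the justification for the secondary outcomes is that they help determine whether the drug improves other symptoms and "that buspirone is safe to use in adult gastroparesis patients".

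Section 9.4.4 sets out the analysis:

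- The participant-level AE tables cover any AE, number of AEs and highest grade. They "will be displayed by treatment group along with p-values from" the Fisher exact test.
- The next paragraph of that section adds arm-level rates of AEs and hospitalizations, counted per event and per participant.
- AE counts are fitted with a negative binomial model that allows for over-dispersion. No estimate or interval from it is named for reporting.
- Laboratory, weight and ECG changes are compared by ANCOVA, and categorical outcomes by Fisher's exact test.

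Section 9.4.3 promises two-sided 95% confidence intervals for ANCOVA mean differences and for the odds ratio for binary improvement in the GCSI total score. No section plans a risk difference or interval for AE frequency or for a categorical safety outcome. The sample size in section 9.2 rests on efficacy outcomes only. No expected AE rate and no safety margin is given.

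**The concern.** A statement that a drug is safe has to say which excess risks the data rule out. A p-value above 0.05 does not do that: it may reflect no excess, or an excess that a trial of this size cannot see. Only an interval for the difference separates the two. The plan gives binary efficacy (GCSI improvement) an effect estimate with an interval, but gives binary safety a p-value. If the AE comparison comes out non-significant, the planned output has no stated quantity on which to judge whether a material excess remains possible, and that is the question the safety objective asks.

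**Working it through.** **Inputs from the documents.** 108 participants in two equal groups, so 54 per arm (section 9.2). The safety set is everyone who took at least one dose (section 9.3), so 54 per arm is close to its maximum size. Two-sided alpha of 0.05 is stated for the primary outcome; section 9.4.4 gives no threshold, so 0.05 is assumed for the Fisher tests.

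**The plan's own figure.** With SD 0.8 at each time and correlation 0.55, the SD of change is √(2 × 0.8² × (1 − 0.55)) = √0.576 = 0.759. For a difference of 0.5 at 90% power, n per arm = 2 × (1.96 + 1.2816)² × 0.576 / 0.5² = 48.4, rounded up to 49. The total is 98, and 98 × 1.10 = 107.8, or 108. The stated size is reproduced, and no safety quantity enters it.

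**Chance that a true 20-point excess is non-significant.** For each assumed placebo rate p, with buspirone rate p + 0.20, every possible pair of counts from 54 and 54 was enumerated. The binomial probabilities of the pairs with two-sided Fisher p > 0.05 were then summed.

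| Placebo rate (assumed) | Buspirone rate | Non-significant |
|---|---|---|
| 5% | 25% | 21% |
| 10% | 30% | 33% |
| 20% | 40% | 45% |
| 30% | 50% | 51% |
| 40% | 60% | 55% |
| 50% | 70% | 51% |
| 60% | 80% | 45% |
| 70% | 90% | 33% |

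Smaller excesses are missed more often: 10% versus 20% is non-significant 79% of the time, and 2% versus 10% is 78%.

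**What an interval adds on the same data.** The Newcombe 95% interval for the difference d = p₁ − p₂ is built from the Wilson limits (l, u) of each arm. Its lower limit is d − √[(p₁ − l₁)² + (u₂ − p₂)²] and its upper limit is d + √[(u₁ − p₁)² + (p₂ − l₂)²].

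- 19/54 buspirone versus 11/54 placebo: Fisher p = 0.13; difference 14.8 points; interval −2.1 to +30.7 points.
- 24/54 versus 16/54: p = 0.16; difference 14.8 points; interval −3.3 to +31.7 points.
- 16/54 in both arms: p = 1.0. The proportion is 0.296 with Wilson limits 0.191 and 0.428, so the upper limit is √(0.132² + 0.105²) = 0.169, or 16.9 points.
- No events among 54: the exact one-sided 95% upper bound on that arm's risk is 1 − 0.05^(1/54) = 0.054, or 5.4%.

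All of these comparisons are non-significant, but they leave quite different excess risks open.

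**The case against.** The strongest reply is that this is a reporting detail. Section 9.4.4 does more than print p-values: it gives AE and hospitalization rates by arm, per event and per participant, and a model for counts. A reader could compute the risk difference and its interval from those rates. There are also event-level listings with grade and relatedness, Medical Safety Officer review and DSMB review. All of this is true and softens the point. It does not remove it, because the plan commits to no between-arm estimate for AE frequency, and monitoring during the trial does not supply one for the final report.

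Four stronger readings are tempting, and the documents do not support them.

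- *The missing interval causes the low power.* It does not. The miss rates follow from 54 per arm and would be the same with an interval printed beside the p-value.
- *A 20-point excess is missed about half the time whatever the event.* That needs a placebo rate of roughly 20% to 60%, which may be reasonable for any AE but is an assumption. For uncommon events a 20-point excess would usually be detected, and section 8.2 describes most buspirone AEs as infrequent to rare. The documents also do not single out 20 points as the excess that matters.
- *No safety measure has a planned interval.* Weight, ECG and laboratory changes are listed as secondary outcomes in sections 1.1 and 3. Section 9.4.3 promises a 95% interval for each secondary outcome analysed by ANCOVA. That section's pointer, "Secondary outcomes are listed in" section 9.1, does not show that safety was dropped, because the list there is one of efficacy hypotheses.
- *The plan states that non-significance will be read as safety.* No section says so. The wording about safe use is in a justification column, and the objective itself is phrased more neutrally. The gap is that nothing in the plan prevents that reading or offers a better basis.

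**Conclusion.** The point holds for participant-level AE outcomes and categorical safety outcomes, where a Fisher p-value is the only named between-arm statistic, and for the negative binomial model, which has no stated rate ratio or interval. With 54 per arm, p > 0.05 cannot carry a safety conclusion. A true 20-point excess is non-significant 45% to 55% of the time for placebo rates of 20% to 60%, 33% at 10% and 21% at 5%. Equal observed counts of 16/54 still leave an excess of up to 17 points possible. These figures rest on assumed placebo rates, an assumed two-sided 0.05 threshold and the full 54 per arm. The primary efficacy conclusion is untouched. What changes is what the trial can say on a stated secondary objective, and the change is worth making.

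**What to change.** In section 9.4.4:

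- For any AE, any serious AE, any AE of grade 3 or higher, and categorical ECG and laboratory outcomes, report the proportion in each arm and the risk difference (buspirone minus placebo) with a two-sided 95% interval, for example Newcombe's. Where an arm has no events, give the exact upper bound.
- Report the negative binomial rate ratio with its 95% interval.
- State that safety conclusions will rest on these intervals, and that p > 0.05 will not be taken as absence of harm.
- For the ANCOVA safety differences, a cross-reference to the interval already promised in section 9.4.3 is enough.

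In section 3, reword the justification so that the aim is to estimate the excess risk of AEs with buspirone and its uncertainty.

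The cost is a few sentences and some table columns, with no new data or participants. The drawback is a less definite safety statement, because the intervals will be wide: with equal rates in the two arms, the half-width 1.96 × √(2p(1 − p)/54) is about 11 points at a 10% rate, 17 at 30% and 19 at 50%.
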